7.1. Primary Effectiveness Endpoint

The occurrence of non-effective LAA closure defined as any peri-device flow > 5mm demonstrated by TEE/CT/MRI at First Follow-up.

7.2. Primary Safety Endpoint

The occurrence of one of the following events between the time of implant and within 7 days following the procedure or by hospital discharge, whichever is later: all-cause death, ischemic stroke, systemic embolism, or device or procedure related events requiring open cardiac surgery or major endovascular intervention such as pseudoaneurysm repair, AV fistula repair, or other major endovascular repair.

NOTE: Percutaneous catheter drainage of pericardial effusions, snaring of an embolized device, thrombin injection to treat femoral pseudoaneurysm and nonsurgical treatments of access site complications will be captured as adverse events (AEs), and are excluded from this endpoint.

7.3. Secondary Effectiveness Endpoint

The occurrence of ischemic stroke or systemic embolism at 12 months from the time of implant.

7.4. Additional analysis

The occurrence of stroke (including ischemic and/or hemorrhagic), cardiovascular death (cardiovascular and/or unexplained cause) and systemic embolism.

8. Study Design

This study is a prospective, non-randomized, multi-center observational study.

8.1. Scale and Duration

Up to 50 subjects at up to 5 investigational centers in Hong Kong will be enrolled in the study. Each investigational site might have up to 2 roll-in subjects, which is included in the 50 total subjects.

Enrollment is expected to be completed in approximately 12 months and each subject is expected to be followed for approximately 12 months with primary endpoints collected at First Follow-up $(30 \sim 100 \text{ days})$; therefore the total study duration is estimated to be approximately 24 months.

The study duration for each subject is expected to be approximately 12 months.

8.2. Justification for the Study Design

WATCHMAN FLX is new generation of the WATCHMAN product, and its safety and effectiveness in being verified in the PINNACLE FLX study conducted in the U.S. Although it is assumed that ethnic difference might not play an important role in the performance of the left atrial appendage closure, this HK FLX study is designed to observe the safety and effectiveness of the WATCHMAN FLX in Hong Kong area.

This is an observational data collection designed to compile real-world data for WATCHMAN FLX in Hong Kong. The implant of the device is decided according to the patient clinical indications, regardless of participation in the study. The post-implant TEE (or alternative imaging methods) is also a clinical standard after the procedure to ensure sealing and exclude thrombus on the device prior to stop dual platelet inhibition or warfarin. The patients are followed per standard of care including the 12-Month Follow-up, which is mainly to collect adverse events, so no additional examination or procedure is required by the study other than standard clinical practice.

9. Subject Selection

9.1. Study Population and Eligibility

Any patient, who meets all the inclusion criteria, does not meet any of the exclusion criteria, and who provides written informed consent may be enrolled in the study. The subjects selected for participation will be from the investigator's general patient population. The investigator has the responsibility for screening all potential patients and selecting those who meet study inclusion/exclusion criteria as described in sections 错误!未找到引用源。 and 0.

9.2. Inclusion Criteria

A subject may be enrolled in the study if all of the following inclusion criteria are met, provided no exclusion criteria (see section 9.3) are met:

- 1. Patients who are eligible for a WATCHMAN FLX device according to current international and local guidelines (and future revisions) and per physician discretion;
- 2. Patients who are willing and capable of providing informed consent, participating in all testing associated with this clinical investigation at an approved clinical investigational center;
- 3. Patients whose age is 18 years or above, or of legal age to give informed consent specific to state and national law.

9.3. Exclusion Criteria

Subjects will be excluded from the study if they meet any of the following criteria:

- 1. Patients who are currently enrolled in another investigational study or registry that would directly interfere with the current study, except when the patient is participating in a mandatory governmental registry, or a purely observational registry with no associated treatments. Each instance should be brought to the attention of the sponsor to determine eligibility.
- 2. Women of childbearing potential who are, or plan to become, pregnant during the time of the study (method of assessment upon physician's discretion);
- 3. The subject is unable or not willing to complete follow-up visits and examination for the duration of the study.

10. Subject Accountability

10.1. Enrollment

Subjects who meet the eligibility criteria as per 错误!未找到引用源。 and 0, have signed and dated the Informed Consent Form and actually undergo a WATCHMAN FLX implant procedure are considered enrolled in the study. Baseline data from subjects who meet the eligibility criteria as per 错误!未找到引用源。 and 0, have signed and dated the Informed Consent Form but do not eventually undergo a WATCHMAN FLX implant procedure are

Form/Template 92120219_Rev/Ver G Confidential WATCHMAN FLX HK Protocol, 92427834, Rev/Ver D Page 22 of 51 collected for epidemiological reasons, to better characterize the population. The start of the WATCHMAN FLX implant procedure is considered the insertion of the WATCHMAN FLX

10.2. Withdrawal

Access Sheath.

Every effort should be made to retain subject enrollment for the duration of the study. During the informed consent process subjects should be fully informed of the data collection requirements and duration, and should only be enrolled if willing to fully participate in it. All subjects enrolled in the clinical study must be accounted for and documented. Reasons for withdrawal may include physician discretion, subject choice to retire consent, loss to follow-up, or death. In the event a subject does decide to withdraw from the study, every effort should be made to obtain full information on any on-going adverse events.

Subjects should only be considered lost to follow-up after significant effort has been made to contact the subject. At a minimum there should be 3 documented telephone contact attempts and one certified letter sent to the subject's last known residence. Subject withdrawal and lost to follow-up will be documented on the "End of Study" CRF. For subjects who are "lost-to-follow-up" the investigator/center should make documented attempts to contact the subject prior to completion of the applicable CRF. Additional data may no longer be collected after the point at which a subject has been withdrawn from the study or withdraws his/her consent, for whatever reason. All open adverse events should be closed or documented as chronic. Data collected up to the point of subject withdrawal may be used, unless any local regulations apply which require removal of the data.

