11.7. Study Completion

Each subject will be followed for 12 months after the implant. In case of premature termination of the study, data collection will stop accordingly. As this is an observational study, subjects will be managed according to standard of care as per centers practice following termination/completion of the study.

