21.1. Safety Monitoring Process

The BSC Medical Safety group will provide safety oversight and classify individual events. During regularly scheduled monitoring visits, clinical research monitors will support the dynamic reporting process through their review of source document information.

The BSC Medical Safety group includes physicians with expertise in Electrophysiology (EP), and/ or Cardiology, as well as other healthcare professionals with the necessary therapeutic and subject matter expertise to evaluate and classify the events into the categories outlined above.

22. Suspension or Termination

This study may be terminated at any time. Upon completion or termination, all data must be returned to the sponsor.

23. Publication Policy

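### Section 10.2 stops all data collection after any withdrawal, even where consent stands, and offers no ongoing or unknown outcome for open adverse events

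*Protocol*

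**What the plan says.** Protocol 10.2 sets out who may be withdrawn: "Reasons for withdrawal may include physician discretion, subject choice to retire consent, loss to follow-up, or death". It contains three instructions that bear on this point.

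- Where the subject decides to withdraw, "every effort should be made to obtain full information on any on-going adverse events".
- "Additional data may no longer be collected after the point at which a subject has been withdrawn from the study or withdraws his/her consent". The clause goes on to say that this applies for any reason.
- "All open adverse events should be closed or documented as chronic".

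Data gathered before withdrawal may be used, subject to local regulations.

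Three other places deal with how long events are collected.

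- Protocol 10.3 ends adverse event collection for Attempt subjects at withdrawal. Implant subjects are followed on schedule.
- Protocol 20.1, Table 8, requires adverse event and SAE reporting until the study ends, and states no exception for withdrawn subjects.
- SAP 4.3 follows screen failures who have an adverse event from diagnostic testing or medication changes for 45 days from onset, or until it resolves.

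**The concern.** The ban names two triggers separately: being withdrawn, and withdrawing consent. It therefore covers subjects whose consent still stands. Only withdrawal of consent, or a local legal rule, clearly requires collection to stop. Protocol 8.2 and 18.1 describe the visits as standard care, so for the other withdrawals the information may well exist at the site and would be left unused.

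The instruction on open events adds a smaller problem. An acute event that is unresolved at exit is not closed, and it is not necessarily chronic. The text offers no third label.

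At stake are the secondary endpoint (ischemic stroke or systemic embolism at 12 months), the additional analysis of stroke, cardiovascular death and systemic embolism, and the final outcome of ongoing events. In a study of at most 50 subjects, a single event moves a rate visibly.

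**Working it through.** **Step 1: reach of the ban.** Physician discretion is a listed reason for withdrawal. The ban applies when a subject is "withdrawn from the study or withdraws his/her consent, for whatever reason". Taken together, a subject withdrawn by the physician with consent intact yields no further data.

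**Step 2: comparison with the other instructions.**

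| Place | Who | How long events are collected |
|---|---|---|
| Protocol 10.2, ban | Any withdrawn subject | To the point of withdrawal |
| Protocol 10.2, full information | Subject who decides to withdraw | Every effort; no end point given |
| Protocol 10.3 | Attempt subject | To the point of withdrawal |
| Protocol Table 8 | No exception stated | To the end of the study |
| SAP 4.3 | Certain screen failures | 45 days from onset, or to resolution |

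As written, a screen failure with a qualifying event can be followed for longer than a device recipient who is withdrawn with an event still open.

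**Step 3: what the analysis does with the loss.** SAP 7.2 takes the date on the End of Study form as last follow-up. SAP 7.3 builds the 1-year rate from subjects with an event, plus subjects who are event-free with last follow-up at day 335 or later. A subject withdrawn event-free before day 335 therefore leaves the denominator, and a later event never enters the numerator. A subject with a recorded event before withdrawal stays in both.

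**Step 4: illustration.** Exact 95% limits for x events in n subjects are the 2.5% quantile of Beta(x, n-x+1) and the 97.5% quantile of Beta(x+1, n-x).

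- Check against protocol Table 4: 2/50 = 4.0%, limits 0.5% and 13.7%. This reproduces the table.
- Suppose one of the two subjects was withdrawn event-free before day 335 and the stroke came later. The numerator is 2-1 = 1 and the denominator 50-1 = 49. Then 1/49 = 2.0%, limits 0.1% and 10.9%.
- SAP 4.1 excludes roll-in subjects from the secondary endpoint, so 50 is a ceiling. Taking 40 as an assumed lower case (the documents estimate at least 40 for the primary analysis sets): 2/40 = 5.0% (0.6-16.9%) becomes 1/39 = 2.6% (0.1-13.5%).

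In both cases the estimate falls by about half. The assumption of two true events with one missed is mine. The documents give neither a withdrawal rate nor an expected 12-month event count for this study.

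**The case against.** Several points on the other side stand.

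- A reader might infer that 10.2 flatly contradicts itself. It does not. The full-information sentence applies when the subject decides to withdraw, so it is not triggered by physician discretion. Where it is triggered, the two sentences can be read in order: gather the information, then stop. This is a tension, plus a gap for physician withdrawal.
- A reader might infer that sites are forced to record false outcomes. The sentence on open events says should, and the outcome codes of the adverse event form are not in the documents. The chronic label may in practice serve for unresolved events. Misrecording is possible but not established.
- Events recorded before withdrawal still count. A second stroke after withdrawal changes no occurrence endpoint; only a first event, a death or the final outcome of an open event is exposed. For an Implant subject withdrawn after day 7 and after discharge, the primary safety endpoint is unaffected.
- Nothing says that physicians withdraw device recipients because of complications. Section 10.2 opens by asking for every effort to retain subjects, and the withdrawals described in detail in 10.3 concern Intent and Attempt subjects, who received no device.
- A reader might extend the point to early termination, from 11.7: "In case of premature termination of the study, data collection will stop accordingly". That sentence does not say that collection stops at once for implanted subjects, and no safety-based stop or interim analysis is described. It does not support a claim that safety data would be discarded.

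None of this removes the ban itself, which is stated as a rule and does not depend on consent.

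**Conclusion.** The point holds as a design weakness that is cheap to correct. Followed as written, 10.2 gives up outcomes that may be available from routine care in subjects who have not withdrawn consent, and SAP 7.3 then drops those who were event-free before day 335 from the 12-month rate. The 10.2 rules also need reconciling with protocol 10.3, protocol Table 8 and SAP 4.3.

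The size cannot be derived from the documents. One missed stroke would roughly halve the 12-month estimate in the illustration, while the intervals remain wide and overlap heavily. Downward bias requires withdrawal to be related to later outcome or to complications, which is plausible but not shown. The study is descriptive, with no hypothesis test, so no formal decision turns on this.

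**What to change.** 1. In 10.2, limit the ban on further data to withdrawal of consent and to what local law requires.
2. For other withdrawals where consent stands, keep collecting endpoint events, SAEs and vital status from routine records to month 12.
3. Replace the two options for open events with three: resolved, ongoing at exit, or unknown, each with the date last known.
4. Reconcile 10.2 with the Attempt rule in 10.3, the reporting period in Table 8 and the screen-failure follow-up in SAP 4.3, so that one rule states how long events are collected for each class of subject.

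The cost is a protocol amendment, an outcome code on the adverse event form, consent-form wording with ethics approval, and slightly longer data collection for a few subjects. Whether current consent already covers record review after withdrawal cannot be judged here, because the consent form is not among the documents. The change concerns data collection only and adds no visit or test.

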10.3. Subject Status and Classification

Consent Ineligible

A subject who has signed informed consent but is found to not meet eligibility criteria will be classified as "**Consent Ineligible**". There are no FU or adverse event reporting requirements for consent ineligible subjects. Subjects determined to be Consent Ineligible according to statements above do not count towards the enrollment ceiling and will not be used for analysis of the endpoints. The original signed Informed Consent must be maintained in the center's administrative file.

Intent

A subject who signs informed consent, meets eligibility criteria, but then does not undergo an implant of a WATCHMAN FLX device will be classified as "Intent". This definition includes subjects that do not meet echocardiographic criteria for a WATCHMAN FLX implant at the implant TEE/CT/MRI evaluation (e.g. a thrombus has developed in the LAA, inappropriate LAA size). These patients may be withdrawn immediately, unless re-assessment of the criteria is planned. If subjects are re-assessed for WATCHMAN FLX implant, as per physicians' discretion, then a reconsent must be obtained for participating in the registry.

Subjects who have been consented, but not yet implanted at the time of enrollment closure will also be classified as **Intent**. There are no FU or adverse event reporting requirements for Intent subjects. Intent subjects do not count towards the enrollment ceiling and will not be used for analysis of the endpoints. The original signed Informed Consent must be maintained in the

center's patient file. For these subjects, the eCRFs in the "Baseline" folder and a "Patient Status" form must be completed. Subjects who become Intents due to death before the implant procedure must have the death documented.

Attempt

A subject who signs informed consent, meets eligibility criteria and has had the WATCHMAN FLX Access Sheath inserted to implant the device, but eventually does not receive a WATCHMAN FLX device will be classified as "**Attempt**". These subjects may be withdrawn, unless a re-implant of a study device is planned, per physician discretion. If subjects are re-assessed for WATCHMAN FLX implant, as per physicians' discretion, then a reconsent must be obtained for participating in the registry. These subjects will be handled as "Implant" (see next section), if the re-implant is successful. Subjects who eventually have not received a WATCHMAN FLX device at the time of enrollment closure will remain classified as "Attempt" and be withdrawn. There are no FU requirements for Attempt subjects; however, adverse events will be collected up to the point of subject withdrawal. Attempt subjects count towards the enrollment ceiling and will be used for analyses of the endpoints. The original signed Informed Consent must be maintained in the center's study file and the following forms must be completed:

- eCRFs in the "Baseline" and "Implant" folders
- "Adverse Event" forms for any adverse event that occurs after signing the Informed Consent, up to the point of subject withdrawal.
- "Patient Status" form for withdrawal, when applicable.

The date at which the patient status form has been completed will be the point of subject withdrawal.

Implant

A subject who is successfully implanted with the WATCHMAN FLX device will be classified as "**Implant**". These subjects are followed in accordance with the FU schedule and included in all study analyses. All applicable case report forms per the protocol must be completed. The original signed Informed Consent and any relevant documentation must be maintained in the center's patient file.

Roll-in and non-roll-in

Each site might have up to 2 roll-in subjects if the site has never implanted a WATCHMAN FLX before. Roll-in subjects should be decided before the implant procedure, and might be classified as **Attempt** or **Implant** after the procedure. Roll-in subjects are enrolled and counted to the ceiling of the sample size. Other enrolled subjects are defined as non-roll-in.

Figure 2: Subject Status and Data Collection Flow Chart

11. Study Methods

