11.1. Data Collection

To ensure data quality and completeness, all required data will be recorded on case report forms (CRFs) provided by the sponsor. Data will be entered onto electronic case report forms by the investigational site or designee. Case Report Forms should be completed accurately during and in a timely manner after any visit in the study. The Principal Investigator or appointed designee must review the case report forms and sign them, certifying their accuracy. Completed case report forms should be submitted to the sponsor within two weeks of completion of a study visit.

Each patient will be followed for a period of 12 months after implant according to the schedule and standard practice at the enrolling centers. There will be no additional procedures, for subjects who participate in the study. Subjects are expected to be followed at implant, then at First Follow-up ($30 \sim 100$ days), and 12-Month Follow-up (365 ± 30 days) post-implant. An intermediate visit may be scheduled in a number of patients, per physician discretion.

For subjects who are not scheduled to visit the clinic for a follow-up, a subject contact (e.g. phone call) will ensure capture of the endpoint related information, however it is strongly recommended to perform an in-office visit for at least the First Follow-up visit.

Table 3 provides an overview of the data to be collected at each visit.

				Follow Up	
Data Collected	Enrollment	Implant	First (30 ~ 100 days) Office	12-Month (365 ± 30 days) Office/Phone	Additional Office/Phone
Informed Consent	Х				
Inclusion/Exclusion	Х				
Demographic data	Х				
Medical History	Х				
LAA imaging (TEE/CT/MRI)	X ^{a,b}	Xa	Х	Xa	X ^a
Medication Regimen	Х	Х	Х	Х	Х
Current status and Vital Signs	Х	Х	Х	Х	Х
Adverse Event and Device Deficiency Reporting	X	X	X	X	Х

Table 3: Data Collection Overview

^a collected only if performed

^b within 3 calendar days prior to implant

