11.4. LAA Imaging (e.g. TEE/CT/MRI)

Prior to implantation with the WATCHMAN FLX device, an Enrollment TEE (or alternative imaging method) is a clinical standard to confirm there is no thrombus in the LAA or left atrium. If an intracardiac thrombus is visualized by echocardiographic imaging, the patients will not be implanted. Re-assessment may be scheduled per physician's discretion.

The Implant LAA imaging will also allow the investigator to obtain proper measurements of the LAA to correctly size the device, confirm device release criteria are met prior to device release, and to confirm adverse events have not occurred during the implant procedure (i.e., pericardial effusion). If an intracardiac thrombus is visualized by echocardiographic imaging, the patients will not be implanted. Re-assessment may be scheduled per physician's discretion.

The Follow-up LAA imaging is a clinical standard after the WATCHMAN FLX procedure, it is conducted to assess flow through and around the WATCHMAN FLX device, to ensure sealing and to verify there is no thrombus on the surface of the device prior to stopping dual platelet inhibition or warfarin. Additional LAA imaging may be conducted at the discretion of the investigator and according to center's practice.

Certain information from TEE/CT/MRI conducted during the course of the study will be captured on the study case report forms, including: heart rhythm; valve status; pericardial status; atrial septum characteristics; LAA size and type of anatomy; thrombus assessment.

For measurement of per-device flow:

- Use multiple TEE views (0°, 45°, 90°, and 135°) or 3D-TEE
- Echo colour Doppler TEE: set Nyquist limit to detect low velocity flow (20–30 cm/s). If leak is present, measure only the mosaic (high-velocity) colour of a communicating flow in multiple projections
- Use same settings during implantation and follow-up
- Document largest measurement as size of leak and achieved angle of measurement by TEE or CT/MRI

11.5. *Implant Procedure*

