12.2. Statistical Analysis and Data Sets

There is no hypotheses testing in this small sample size observational study.

The Primary Effectiveness Endpoint is the occurrence of non-effective LAA closure defined as any peri-device flow > 5mm demonstrated by TEE/CT/MRI at First Follow-up.

The Primary Safety Endpoint is the occurrence of one of the following events between the time of implant and within 7 days following the procedure or by hospital discharge, whichever is later: all-cause death, ischemic stroke, systemic embolism, or device- or procedure-related events requiring open cardiac surgery or major endovascular intervention such as pseudoaneurysm repair, AV fistula repair, or other major endovascular repair. Percutaneous catheter drainage of pericardial effusions, snaring of an embolized device, thrombin injection to treat femoral pseudoaneurysm and nonsurgical treatments of access site complications are excluded from this endpoint.

Roll-in subjects are excluded from all Primary Endpoint analyses, and will be treated separately analysis set for the Primary Effectiveness analysis includes implanted subjects with a completed First Follow-up visit. The analysis set for the Primary Safety analyses will be the "intent-to-treat" analysis set, including implanted or attempted subjects. It is estimated that both Primary Effectiveness analysis and Primary Safety analysis dataset will include at least 40 subjects.

For the Primary Effectiveness Endpoint, it might be considered reasonable if up to 3 primary effectiveness endpoint events should occur in this small sample size study.

For the Primary Safety Endpoint, it might be considered reasonable if up to 3 primary safety endpoint events should occur in this small sample size study.

Missing data will not be dealt with systematically in this small sample size study. A tippingpoint analysis might be conducted for the Primary Effectiveness Endpoint to assess the impact of different assumptions about the missing data on interpretation of the results.

For Secondary Endpoint and additional analysis, different data sets could be used exploratively.

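### At sites new to WATCHMAN FLX, roll-in subjects need not be the first consecutive cases and may be named after LAA imaging has been seen, yet they leave the primary analyses

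*Protocol*

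**What the plan says.** Protocol 10.3 sets the entitlement: "Each site might have up to 2 roll-in subjects if the site has never implanted a WATCHMAN FLX before". It sets the timing in one clause: "Roll-in subjects should be decided before the implant procedure". SAP 4.1 repeats both. Roll-ins count towards the ceiling of 50 and may end up classified as Attempt or Implant.

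Protocol 10.1 fixes when the procedure begins: "The start of the WATCHMAN FLX implant procedure is considered the insertion of the WATCHMAN FLX" Access Sheath. The label can therefore be given at any time up to sheath insertion.

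On imaging before that point:
- Protocol 11.4: "Prior to implantation with the WATCHMAN FLX device, an Enrollment TEE (or alternative imaging method) is a clinical standard".
- Protocol 11.1, Table 3, dates the enrollment imaging "within 3 calendar days prior to implant", and marks it as collected only if performed.
- Protocol 10.3 describes subjects found unsuitable "at the implant TEE/CT/MRI evaluation (e.g. a thrombus has developed in the LAA, inappropriate LAA size") who are then classed as Intent. Some imaging results are thus known before a sheath goes in.

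On analysis, Protocol 12.2 states: "Roll-in subjects are excluded from all Primary Endpoint analyses, and will be treated separately". SAP 4.1 extends the exclusion to the secondary endpoint. Both documents expect at least 40 subjects in each primary set, and both call up to 3 events acceptable for each primary endpoint without naming a denominator.

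**The concern.** Roll-in cases normally allow for operator learning. That purpose is served when they are the first cases at a site, because the order of treatment then decides who is excluded. Here the rule is discretionary in number and fixed only by a deadline, and the deadline falls after imaging that can show a difficult appendage. A site that followed the text exactly could give the label to subjects whose anatomy looked unfavourable.

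If anatomy predicts leak or procedural complications, this would lower the reported rates for both primary endpoints. Nothing in the plan would show it:
- Table 3 has no roll-in field.
- SAP 4.3, on control of bias, does not mention roll-ins.
- No primary result is planned with roll-ins included.

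The point matters beyond the local report, because Protocol 6 foresees using the data for registration elsewhere alongside the U.S. study of the device. A reader of that comparison will ask how subjects came to be left out.

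**Working it through.** **Inputs.** Ceiling 50 subjects and up to 5 sites (Protocol 8.1); up to 2 roll-ins per eligible site (Protocol 10.3); at least 40 in each primary set and up to 3 events acceptable (Protocol 12.2); exact confidence limits at n = 50 (Protocol Table 4).

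**1. The plan's own figures.** Maximum roll-ins = 5 × 2 = 10, which is 10/50 = 20%. The remainder is 50 − 10 = 40, which matches the stated minimum. Exact (Clopper–Pearson) limits for x events in n are L = Beta⁻¹(0.025; x, n − x + 1) and U = Beta⁻¹(0.975; x + 1, n − x). For 3/50 this gives 1.25% and 16.55%, agreeing with Table 4 (1.3% and 16.5%) to rounding. The other five rows also reproduce.

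**2. Does the never-implanted condition force first cases?** There are two readings.
- Tested subject by subject, a site loses eligibility after its first implant. A second roll-in would then be possible only if the first had ended without an implant, which sits badly with an allowance of two.
- Tested once, as a description of the site when it joins, two roll-ins are possible but nothing fixes where they fall in the treatment order.

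The condition suggests early cases. The text does not say so.

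**3. Effect on the count at the ceiling.** Suppose all 50 subjects are evaluable, 10 are roll-ins, and 6 events occur.
- All subjects: 6/50 = 12.0%, above 3 events.
- Three events among roll-ins: (6 − 3)/(50 − 10) = 3/40 = 7.5%, exact 95% CI 1.6–20.4%, within 3 events.

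If the 10 roll-ins were chosen independently of outcome risk, the chance that they would hold at least 3 of the 6 events is Σ C(6,k)·C(44,10−k)/C(50,10) for k = 3 to 6. This is 0.0746 + 0.0103 + 0.0006 + (less than 0.0001) ≈ 0.086, or about 9%. The shift can occur without selection. Selection on a prognostic feature would make it more likely.

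**4. Separating selection from exclusion as such.** Step 3 alone does not do this, because any rule that excludes 10 subjects leaves 40. So compare two ways of choosing the same 10. The documents give no event rates by anatomy; the rates below are assumptions. Let 10 of 50 subjects be difficult with event rate d, and the other 40 have rate r.
- Selected (all 10 difficult subjects become roll-ins): P(≤3) = P(Bin(40, r) ≤ 3).
- Independent of difficulty: the number H of difficult subjects left among the 40 is hypergeometric, and P(≤3) = Σ P(H = h)·P(Bin(h, d) + Bin(40 − h, r) ≤ 3).

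| r | d | Overall rate 0.8r + 0.2d | P(≤3 of 40), independent | P(≤3 of 40), selected |
|---|---|---|---|---|
| 3% | 10% | 4.4% | 0.90 | 0.97 |
| 3% | 20% | 6.4% | 0.75 | 0.97 |
| 5% | 15% | 7.0% | 0.69 | 0.86 |
| 5% | 20% | 8.0% | 0.60 | 0.86 |

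Under full selection the expected primary rate falls from the overall rate to r, for example from 6.4% to 3%. These are extremes: every place is used and every difficult case is labelled.

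**The case against.** The case on the other side has several sound parts.

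- **Not every site, and perhaps not any subject.** A reader might infer that any site can label any two subjects. The documents do not support that. Only sites new to the device qualify, and the condition can be read as pointing to first cases. What stands against it is that the order is not stated and the strict reading conflicts with an allowance of two.
- **Anatomy may not be known.** A reader might infer that operators always know the anatomy when they give the label. Enrollment imaging is recorded only if performed, Protocol 11.4 gives its purpose as excluding thrombus, and it assigns LAA measurement to the implant imaging. Knowledge before labelling is possible, not established.
- **Roll-ins are not discarded.** They count to the ceiling, those implanted are followed on schedule, and they are treated separately. This stands. The gap is that no primary result is planned with and without them, and the by-center results in SAP 5.1 do not fill it.
- **No relabelling after the outcome.** The decision must precede the procedure, so a leak or complication cannot prompt it. This is a real safeguard, though the plan asks for no dated record by which to verify it.
- **The benchmark is soft.** There is no hypothesis test, and 3 events is loose descriptive guidance. Crossing it is not a formal pass or fail.
- **Small examples prove little.** 3/50 becoming 1/40 would meet the benchmark either way and would look the same under a first-cases rule. That is why the working compares two ways of choosing the same ten subjects.

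**Conclusion.** The concern holds as a gap in the definition. For sites new to the device, the plan fixes a maximum and a deadline for roll-ins but neither their order nor a dated record, and the deadline falls when imaging may already have been seen. The subjects concerned then leave both primary analyses and, in the SAP, the secondary one.

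The ceiling is 10 of 50 subjects (20%). It requires five open sites, all new to the device, each using both places; the documents do not say how many sites are new. The change from 6/50 to 3/40 further assumes complete endpoint data and three events among roll-ins. It shows what the rule permits and is not a forecast. Any bias also depends on anatomy predicting the endpoints, which the documents do not quantify.

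A reader might go further and infer that difficult cases have been, or are meant to be, moved out. Nothing in either document supports that. The wording is equally consistent with ordinary learning-curve practice that was not written down.

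**What to change.** 1. In Protocol 10.3 and SAP 4.1, define roll-ins as the first one or two consecutive WATCHMAN FLX procedures at a site with no previous implant of the device. State that the condition is judged when the site joins the study.
2. Enter roll-in status in the EDC, with a date, before LAA imaging is reviewed.
3. Report both primary endpoints with and without roll-ins, each with its denominator and exact 95% interval.
4. The amendment history mentions slowed enrollment, so sites may already be active and a prospective rule may come too late for some. For those sites, list each roll-in's position in the site's treatment order. Items 3 and 4 can be added however far enrollment has gone.

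The cost is a sentence in each document, one EDC field and one table, plus the short listing for active sites. The downside is that sites lose discretion over who is a roll-in. The maximum exclusion stays at 10 and the minimum primary set at 40, so no precision is lost.
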